7. Santana LS et al. Transcutaneous electrical nerve stimulation (TENS) reduces pain and postpones the need for pharmacological analgesia during labour: a randomised trial. *J Physiother*. 2016 Jan;62(1):29-34. doi:10.1016/j.jphys.2015.11.002. Epub 2015 Dec 11.

8. Lison F, et al. Transcutaneous Nerve Stimulation for Pain Relief During Office Hysteroscopy: A Randomized Controlled Trial. JF Lisón et al. Obstet Gynecol 129 (2), 363-370. 2 2017.

3. Trial objectives and purpose

To evaluate if TENS is effective in reducing pain during transvaginal oocyte retrieval using conscious sedation

4. Trial design

This is a randomized, double-blinded placebo-controlled trial. Women who are eligible will be recruited and randomized into one of two groups.

- a. Treatment group: conscious sedation with 25 mg IV pethidine and 5mg IV diazepam and active TENS
- b. Placebo group: conscious sedation with 25 mg IV pethidine and 5mg IV diazepam and placebo TENS

5. Selection and withdrawal of subjects

5.1 Inclusion Criteria Women who undergo transvaginal oocyte retrieval who is aged 18 or above will be recruited.

5.2 Exclusion Criteria

Women will be excluded from the study if

- There is only one ovary
- Oocyte retrieval performed on one ovary only
- There are less than three follicles ≥ 16 mm in diameter
- Allergic to pethidine or midazolam
- Previous experience with TENS
- Skin damage or allergy at site of TENS pads application
- History of pacemaker insertion

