5.3 Subject withdrawal criteria

Participation in the study is totally voluntary. The subjects can withdraw from the study at any time and they will receive standard medical care. Their participation may be discontinued in case of severe side effects during the procedure.

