The woman lies on the operative bed in a lithotomy position. 25mg Pethidine and 5mg Diazepam will be given intravenously. The blood pressure and pulse of the woman are checked after the drug administration and the oxygen saturation is monitored continuously throughout the procedure. 10ml 1% lignocaine is injected to the paracervical region by the operating surgeon with a 21-gauge needle after cleansing the vagina and cervix with chlorhexidine. Under transvaginal ultrasound guidance, a 16-gauge ovum aspiration needle is introduced. Aspiration of follicles is performed with a suction pressure of 100 mmHg.

Assessment of pain level

The women will be asked to rate the pain according to a 100mm linear visual analogue scale. They will be asked to rate the pain level related to insertion of an intravenous cannula and the anticipated pain level of the retrieval.

Then women will be asked to rate

1. The maximum vaginal pain during the procedure
2. The maximum abdominal pain during the procedure
3. Pain immediately after the procedure before they leave the operating room
4. Pain at 1 hour after the procedure

Patient's satisfaction towards pain relief will be assessed before discharge. They will be rated as 5, 'excellent'; 4, 'satisfactory'; 3, 'fair'; 2,'not very satisfactory' and 1, 'totally unsatisfactory'.

Collection of data

Apart from the pain score, patient's satisfaction level, occurrence of side effects, patient's characteristics including age, body mass index, blood pressure, heart rate, past history of dysmenorrhea, chronic pelvic pain, mood disorders will be recorded. The duration of procedure, number of follicle aspirated and experience of surgeons will be documented.

Follow-up

No routine follow-up visits will be arranged solely for the study unless considered necessary by the investigators.

7. Assessment of outcome

The primary outcome will be the pain level during oocyte retrieval experienced by patient.

Secondary outcomes include side effects and satisfaction of patient.

8. Assessment of safety

The use of Pethidine and midazolam has been widely used and proven to be safe. They are the standard medications used in our unit for conscious sedation. Oxygen saturation, heart rate of the patient will be monitored throughout the procedure. Blood pressure will be measured before and after the procedure.

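### The allergy exclusion and safety statement name midazolam, but the trial gives diazepam and paracervical lignocaine, and neither passage covers those two drugs

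*Combined protocol and SAP*

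**What the plan says.** Section 4 defines the treatment arm as "conscious sedation with 25 mg IV pethidine and 5mg IV diazepam and active TENS" and the control arm as "conscious sedation with 25 mg IV pethidine and 5mg IV diazepam and placebo TENS". The procedure text in section 6 agrees: "25mg Pethidine and 5mg Diazepam will be given intravenously". It then adds a local anaesthetic, with no distinction by arm: "10ml 1% lignocaine is injected to the paracervical region".

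The drug-allergy exclusion in section 5.2 reads "Allergic to pethidine or midazolam". The only other allergy criterion there concerns the skin where the TENS pads are placed.

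Section 8 also names midazolam: "The use of Pethidine and midazolam has been widely used and proven to be safe". It continues: "They are the standard medications used in our unit for conscious sedation". Section 5.3 provides a later safeguard: "Their participation may be discontinued in case of severe side effects during the procedure".

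**The concern.** An eligibility rule on drug allergy should list the drugs the participant will be given. Here the rule and the regimen name different benzodiazepines, and the local anaesthetic is absent from the rule altogether.

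What is at stake is participant safety and the coherence of the protocol. A site applying section 5.2 exactly as written could enrol a woman with a known allergy to diazepam or lignocaine and then give her that drug. It would also turn away a woman allergic to midazolam, which the procedure does not use; that second consequence is minor. In addition, the safety assurance in section 8 does not mention the sedative that sections 4 and 6 prescribe.

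The precautions that do exist work regardless of which sedative is used: blood pressure and pulse checks after dosing, continuous oxygen saturation monitoring, and discontinuation under section 5.3. They act once the drugs are being given, so they cannot stand in for screening out a known allergy.

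**Working it through.** No figure in the plan bears on this point, so the check is a comparison of the drug names in the operative sections.

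| Place | Function | Pethidine | Diazepam | Midazolam | Lignocaine |
|---|---|---|---|---|---|
| Section 4, treatment arm | dosing | yes, 25 mg | yes, 5 mg | no | no |
| Section 4, placebo arm | dosing | yes, 25 mg | yes, 5 mg | no | no |
| Section 6, the procedure | dosing | yes, 25 mg | yes, 5 mg | no | yes, 10 ml of 1% |
| Section 5.2 | allergy exclusion | yes | no | yes | no |
| Section 8 | drug-safety statement | yes | no | yes | no |

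1. **Sedative prescribed.** Diazepam appears in 3 of 3 sedative dosing statements and midazolam in 0 of 3. Two of the three are parallel arm definitions that differ only in TENS, so the count shows consistency between sections 4 and 6 rather than three independent confirmations.
2. **Coverage of section 5.2.** The drugs given for sedation and local anaesthesia are pethidine, diazepam and lignocaine. Section 5.2 names 1 of these 3, omits 3 − 1 = 2, and adds 1 that is not given.
3. **Coverage of section 8.** It names 1 of the same 3 drugs. Since its sentence concerns conscious sedation, the fairer denominator is the two sedation drugs, of which it names 1 of 2.
4. **Dose.** The 5 mg dose is attached only to diazepam, and no midazolam dose is stated. Staff therefore cannot settle the matter by reading one name for the other.
5. **Effect on the comparison.** Both arms have identical background drugs, so the naming error does not create a difference between them.
6. **Effect on sample size.** The calculation in section 9 uses a difference of 23.0 − 13.0 = 10, SD 21.0, significance level 0.05 (taken as two-sided, which the plan does not state) and power 0.8. It reproduces: n per arm = 2 × (1.960 + 0.842)² × 21² / 10² = 69.2, rounded up to 70. Allowing for 10% dropout gives 70 / 0.90 = 77.8, or 78 per arm against the stated 80. Correcting the drug names alters none of these inputs.

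**The case against.** The strongest objection is that the documents do not settle which benzodiazepine is intended. Section 8 calls pethidine and midazolam the unit's standard sedation, and the background describes the comparator as standard conscious sedation. If midazolam is the real drug, sections 5.2 and 8 are right on the sedative, sections 4 and 6 are wrong, and the gap over diazepam disappears. This stands as a limit on the direction of the correction, but it does not remove the contradiction. The text as written prescribes diazepam, and the lignocaine gap remains whichever sedative is meant.

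A second objection is that leaving out lignocaine is incompleteness rather than inconsistency, since no passage names a different local anaesthetic or claims that section 5.2 lists every drug. The distinction is fair. The consequence is the same, though: a drug given to every woman is not covered by the allergy exclusion.

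A third is that experienced clinicians would ask about allergies anyway. They may, but the protocol describes no such check, so none can be credited or ruled out. The point is confined to the written criteria.

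Finally, excluding a woman allergic to midazolam from a diazepam trial is a reasonable precaution, and a class-wide benzodiazepine exclusion would keep her out too. That is accepted, and the case does not rest on it.

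**Conclusion.** The concern holds and should be fixed. The written allergy exclusion does not match the written regimen: it omits two of the three drugs given for sedation and local anaesthesia and names one that is not given. The safety statement has the same mismatch on the sedative.

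This is an eligibility and safety defect, not a threat to the TENS estimate. It causes no bias between arms and no change to the sample size or analysis. The number of women who might be affected cannot be derived, because the documents give no allergy frequencies and do not describe clinical allergy screening.

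The statement that diazepam allergy is uncovered assumes that the dosing statements in sections 4 and 6 are correct. The conclusion on lignocaine does not need that assumption. The opening part of the document was not available for this check. It might explain where midazolam came from, but it would not correct section 5.2.

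**What to change.** - **All sections.** Decide which sedative is used and name it consistently in sections 4, 5.2, 6 and 8. On the current dosing statements this is diazepam.
- **Section 5.2.** Replace the drug-allergy item with one that covers everything given, for example: known allergy to pethidine, to diazepam or any other benzodiazepine, or to lignocaine.
- **Section 8.** Rewrite the safety statement so that it names the drugs the trial gives. If midazolam is the unit's usual sedative and diazepam was chosen for the trial, say so.

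If diazepam is intended, the cost is a wording amendment to sections 5.2 and 8 and the matching line on any eligibility form, with no change to procedures, sample size or analysis. If midazolam is intended, sections 4 and 6 must be corrected instead and a midazolam dose stated; lignocaine still has to be added to section 5.2.

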5.3 Subject withdrawal criteria

Participation in the study is totally voluntary. The subjects can withdraw from the study at any time and they will receive standard medical care. Their participation may be discontinued in case of severe side effects during the procedure.

5.4 Criteria for exclusion from secondary analysis

None

6. Treatment of subjects

Women who are indicated to undergo IVF in our center will be assessed for eligibility for the study. Written consent will be obtained from those who agreed to join the study.

Randomization

Eligible women recruited will be randomized according to a computer-generated randomization list prepared by a designated research staff into one of the two groups on the day of oocyte retrieval:

1. Patient with both conscious sedation and active TENS
2. Patient with conscious sedation and placebo TENS

Blinding

Both the women and the physician performing the procedure will be blinded from the group allocation.

Checking of effectiveness of blinding will be done by asking the patient and the physician after the procedure as to which group they think the women is in.

The procedure

Women will receive ovarian stimulation according to the departmental Standard Operating Procedures. Ovarian stimulation will be monitored by ultrasound. Human chorionic gonadotrophin or an agonist (decapeptyl) will be given when the dominant follicle is at least 18mm and there are three more follicles of at least 16mm. Oocyte retrieval will then be arranged 36 hours later.

Prior to oocyte retrieval, two sets of self-adhesive electrodes will be placed on the women back on each side of the spine at T10 to S4 level. Instructions on how to titrate the TENS amplitude to the desired level that gives a strong non-painful electrical paraesthesia will be given to the women by the research nurse who is unaware of the group allocation. TENS therapy will start 5 minutes before the procedure and stop 5 minutes after the removal of oocyte aspiration needle. The TENS machine used in the study will be the Endomed 482 that delivers biphasic pulsed currents using pulse duration of 400 μ s and pulse frequencies between 80-100 pulses s⁻¹. The women in the treatment group will be given a TENS machine with electrodes emitting impulses while those in the placebo group will be given a TENS machine with electrodes that is not emitting any impulses.

The woman lies on the operative bed in a lithotomy position. 25mg Pethidine and 5mg Diazepam will be given intravenously. The blood pressure and pulse of the woman are checked after the drug administration and the oxygen saturation is monitored continuously throughout the procedure. 10ml 1% lignocaine is injected to the paracervical region by the operating surgeon with a 21-gauge needle after cleansing the vagina and cervix with chlorhexidine. Under transvaginal ultrasound guidance, a 16-gauge ovum aspiration needle is introduced. Aspiration of follicles is performed with a suction pressure of 100 mmHg.

Assessment of pain level

The women will be asked to rate the pain according to a 100mm linear visual analogue scale. They will be asked to rate the pain level related to insertion of an intravenous cannula and the anticipated pain level of the retrieval.

Then women will be asked to rate

1. The maximum vaginal pain during the procedure
2. The maximum abdominal pain during the procedure
3. Pain immediately after the procedure before they leave the operating room
4. Pain at 1 hour after the procedure

Patient's satisfaction towards pain relief will be assessed before discharge. They will be rated as 5, 'excellent'; 4, 'satisfactory'; 3, 'fair'; 2,'not very satisfactory' and 1, 'totally unsatisfactory'.

Collection of data

Apart from the pain score, patient's satisfaction level, occurrence of side effects, patient's characteristics including age, body mass index, blood pressure, heart rate, past history of dysmenorrhea, chronic pelvic pain, mood disorders will be recorded. The duration of procedure, number of follicle aspirated and experience of surgeons will be documented.

Follow-up

No routine follow-up visits will be arranged solely for the study unless considered necessary by the investigators.

7. Assessment of outcome

The primary outcome will be the pain level during oocyte retrieval experienced by patient.

Secondary outcomes include side effects and satisfaction of patient.

8. Assessment of safety

The use of Pethidine and midazolam has been widely used and proven to be safe. They are the standard medications used in our unit for conscious sedation. Oxygen saturation, heart rate of the patient will be monitored throughout the procedure. Blood pressure will be measured before and after the procedure.

TENS is a non-invasive and non-pharmacological pain relief method. The side effects are minimal including possible allergy to the skin pads, soreness in case of overuse and having an unpleasant sensation if the energy is set too high. The intensity of the TENS machine will be controlled by the patients thus minimizing the possibility of unpleasant sensation.

9. Statistics

Sample size calculation

According to our previous study, the pain level of the retrieval using conscious sedation alone was 23.0 ± 21.0 (mean \pm SD) on a 100-point visual analogue scale. Effect size is estimated based on recommendations for a minimum clinically relevant change of 10 mm on a 0–100 mm VAS for pain. Assuming the pain level is reduced from 23.0 to 13.0 on a 100-point visual analogue scale following TENS, the sample size required would be 70 in each

treatment arm to give a test of significance of 0.05 and a power of 0.8 (Sigmastat, Jandel Scientific, U.S.A.). A total of 160 subjects or 80 subjects in each treatment group are needed if we anticipated a dropout rate of 10%

Statistical analysis

Demographic features between the two groups will be compared. Comparison of categorical variables between groups will be done using X² - test. For continuous variables, the Student's t-test and Mann-Whitney U-test will be used for parametric and non-parametric data, respectively. All statistical analyses will be performed using the Statistical Program for Social Sciences, SPSS and MedCalc software.

10. Direct access to source data / documents

The investigators permit trial-related monitoring, audits, IRB/IEC review and regulatory inspections, providing direct access to source data/documents.

11. Quality control and quality assurance

Patients will be managed by the clinicians who have appropriate experience in performing transvaginal oocyte retrieval.

12. Ethics

Ethics approval for the current study will be obtained from the joint Institutional Review Board of the University of Hong Kong and Queen Mary Hospital. Written consent will be obtained from recruited subjects. Their participation is totally voluntary. They can withdraw from the study at any time.

13. Data Handling and record keeping

All data will be stored in locked computer files that are accessible only to the investigators and research staffs involved in the study. The principal investigator will be responsible for data management including data coding, monitoring and verification.

14. Financing and insurance

The study will be financed by the Department of Obstetrics and Gynaecology, the University of Hong Kong.

15. Publication policy

The findings of this study will be submitted for consideration for publication in peer-reviewed scientific journal.

16. Supplements

The study will be conducted in compliance with the Declaration of Helsinki and Good Clinical Practice (ICH-GCP).

17. We certify that the information given is complete and accurate to the best of our knowledge.

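### Surgeon experience is recorded for each case but given no role in the primary comparison: a modest, avoidable loss of precision, not a bias

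*Combined protocol and SAP*

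**What the plan says.** Section 6 (Collection of data) states: "The duration of procedure, number of follicle aspirated and experience of surgeons will be documented". It gives no categories of experience and does not say how the variable will be used.

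Section 6 (Randomization) says only this about allocation: "Eligible women recruited will be randomized according to a computer-generated randomization list prepared by a designated research staff". It takes place on the day of retrieval. No stratification, blocking or minimisation is described. Section 6 (Blinding) adds: "Both the women and the physician performing the procedure will be blinded from the group allocation".

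Section 6 (The procedure) has the operating surgeon give the paracervical lignocaine, after which the follicles are aspirated. Section 7 defines the main endpoint: "The primary outcome will be the pain level during oocyte retrieval experienced by patient".

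Section 9 (Statistical analysis) offers a chi-square test for categorical variables, and Student's t or Mann-Whitney for continuous ones. It names no covariate model and no stratified test. Its stated check of balance is: "Demographic features between the two groups will be compared". Section 11 requires operators with appropriate experience and sets no threshold.

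**The concern.** The operator gives the local block and performs the procedure during which the primary outcome arises, so operator experience is a plausible predictor of the pain score. The plan collects it and then assigns it no analysis.

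Two things are at stake. First, any variation in pain between operators stays in the error term, although a variable already on the data form could remove it. The planned power is only just 80%, so there is little reserve. Second, if the arms differ visibly in operator mix once the data are in, an adjusted analysis chosen at that stage cannot be told apart from a post-hoc choice. Naming the adjustment beforehand avoids that.

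**Working it through.** **Inputs from section 9.** Control pain 23.0 with SD 21.0 mm, target difference 10 mm, significance level 0.05 (sidedness not stated), power 0.80, 70 per arm before dropout, 80 per arm after 10% dropout.

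**Inputs assumed, because the documents do not give them.** Share of cases done by less experienced operators, p = 0.3 to 0.5. Difference in mean pain between operator levels, D = 5 to 15 mm. The SD of 21 is taken to include variation between operators.

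**Step 1: the plan's own figure.** For a two-sided 5% t-test with difference 10 and SD 21, solving for 80% power gives n = 70.2 per arm, which agrees with the stated 70. Power at exactly 70 is 79.9%. A one-sided test would need 55, so the plan's calculation is two-sided. Allowing for dropout, 70 / 0.9 = 77.8, so 78 per arm; the stated 80 is slightly more generous.

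**Step 2: chance imbalance in operator mix.** The SD of the between-arm difference in the share of less experienced operators is sqrt(2p(1-p)/70).

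- p = 0.3: sqrt(0.42/70) = 0.077; times 1.96 = 15.2 percentage points
- p = 0.5: sqrt(0.50/70) = 0.085; times 1.96 = 16.6 percentage points

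**Step 3: resulting shift in the pain difference.** Shift = D x imbalance.

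| D (mm) | 95% limit, p = 0.3 | 95% limit, p = 0.5 |
|---|---|---|
| 5 | 0.76 mm | 0.83 mm |
| 10 | 1.52 mm | 1.66 mm |
| 15 | 2.28 mm | 2.48 mm |

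These limits are 8% to 25% of the 10 mm target. They are the edge of the range: at D = 10 and p = 0.5 the SD of the shift is 0.85 mm.

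**Step 4: comparison with the standard error.** The standard error of the unadjusted difference is 21 x sqrt(2/70) = 3.55 mm, so the 95% half-width is 1.96 x 3.55 = 7.0 mm. With p = 0.5, operator mix contributes D²p(1-p)/441 of that variance: 6.25/441 = 1.4% at D = 5, 25/441 = 5.7% at D = 10, and 56.25/441 = 12.8% at D = 15.

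**Step 5: power with adjustment.** Residual variance = 441 - D²p(1-p), with 70 per arm and a t-based calculation that ignores the one degree of freedom lost.

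| D (mm) | Residual SD, p = 0.5 | Power, p = 0.3 to 0.5 |
|---|---|---|
| none (unadjusted) | 21.00 | 79.9% |
| 5 | 20.85 | 80.4% |
| 10 | 20.40 | 81.8% to 82.1% |
| 15 | 19.62 | 84.2% to 85.0% |

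**Step 6: simulation check.** With 10,000 trials per setting, 70 per arm and p = 0.5, the unadjusted t-test had type I error 0.047 to 0.049 over D = 5 to 15 mm, and power of about 0.80 at each D. The adjusted test also held its level (0.046 to 0.048), with power 0.80, 0.81 and 0.85 at D = 5, 10 and 15 mm.

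**Step 7: a single unlucky trial.** If the realised imbalance sits at the adverse 95% limit with p = 0.5, approximate unadjusted power falls from 0.80 to 0.73, 0.65 and 0.56 for D = 5, 10 and 15 mm. Favourable imbalances offset this on average, which is why overall power stays near 0.80.

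**The case against.** A reader might infer that an operator imbalance could create or conceal the TENS effect. The documents do not support that. Allocation is random and the operator is blinded, so operator mix differs between arms only by chance, and the standard error of 3.55 mm already allows for it. If the SD of 21 includes operator variation, the planned 70 per arm has already paid for it. A shift of 5 mm, half the target, at D = 10 and p = 0.5 would need a 50-point imbalance, which is 5.9 SDs and has probability of about 3 in a billion. This part of the objection stands in full.

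The assumed sizes can also be called generous. D = 10 mm equals the whole target difference, and 15 mm is 65% of the control mean (15/23.0). All women receive sedation and paracervical lignocaine, and section 11 says that "Patients will be managed by the clinicians who have appropriate experience in performing transvaginal oocyte retrieval". That is fair, and it makes the lower end of the range at least as credible as the upper. It does not make operators uniform, because no threshold is set.

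Two further readings go beyond the text. The first is that the list is known to be unstratified: section 6 simply does not describe how it is built. The second is that experience can never enter a comparison: the generic tests in section 9 would allow it to be tabulated by arm. What is missing is a specified adjusted or stratified analysis.

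Finally, stratified lists add little beyond adjustment at this sample size, and they require the operator to be named before allocation. The protocol places allocation on the day of retrieval but does not say that the operator is fixed by then. This too stands, and it is why stratification is only optional here.

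**Conclusion.** The point holds as a modest gap in precision and pre-specification. The unadjusted comparison is valid, with type I error of about 5%, and no increase in sample size is needed.

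The plan forgoes a gain of roughly 0.5 to 5 power points (79.9% to between 80.4% and 85.0%) and leaves a chance shift of 0.8 to 2.5 mm at the 95% limit uncorrected. Both ranges rest on p = 0.3 to 0.5 and D = 5 to 15 mm, which are assumptions. If experience has no effect on pain, the gain is nil. Adjustment is still worth specifying, because the variable is already collected, TENS cannot affect it, and the cost is close to nothing.

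**What to change.** In section 9, before the first patient:

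- Define two levels of operator experience.
- Make the primary between-arm comparison of pain a linear model (ANCOVA) with treatment and operator experience as terms. If the data call for a rank method, use a van Elteren test stratified by experience, and state in advance the rule for choosing between the two.
- Report operator experience by arm alongside the demographic features.
- State that the primary analysis will not adjust for procedure duration or number of follicles aspirated. Both are recorded after allocation, so they do not have the same standing as operator experience.

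Optionally, in section 6 (Randomization), stratify the list by operator experience where the operator is known before allocation. That needs two lists, and a rule that a woman stays in her randomised stratum if the operator changes.

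The cost of the main change is one degree of freedom and a few lines of text, with no extra patients or data. The gain is negligible if experience does not affect pain.
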